Aim 2a) Determine the effects of *d*CBT-I and CBT-I using a stepped care model for prevention of **2a)** incident depression and **2b)** depression relapse. These aims will be tested by comparing the 1-year rate of depression outcomes of both *d*CBT-I and CBT-I to an attention control group.

Aim 3a) (Exploratory) Evaluate changes in nocturnal rumination as a modifiable behavior (post-treatment) that mediates the effect of insomnia treatment on subsequent depression-risk.

Aim 3b) (Exploratory) Determine the moderating effects of important depression risk-factors (race, SES) on the change in sleep and depression outcomes to establish the critical need and value of early risk-detection and prevention for these groups, and demonstrate the potential greater impact in terms of prevention for individuals with high sleep reactivity.

Figure 1: Study Overview

[figure not shown]
[figure not shown]

Figure 2: Study Timeline and Milestones

Research Strategy

We propose to enroll 500 trial participants (insomnia without depression) in alignment with ongoing data collection procedures within the HFHS network of sites in southeastern Michigan. Baseline assessment will include the utilization of standardized and validated assessment tools for insomnia and major depressive disorder.^{9,71,78-82} Following baseline assessment, insomnia participants will be randomized into Insomnia Treatment (T) or Attention Control (C) groups with a sample of no less than 250 per group, at which point the T group will receive their first treatment with the utilization of Sleepio (www.sleepio.com), an online cognitive behavioral therapy for insomnia *d*(CBT-I).⁸³ Participants will receive 6 weekly sessions of online *d*CBT-I. Specifically, participants are immersed in a fully automated media-rich web environment, driven dynamically by baseline and progress data. The C group will receive sleep hygiene education, which will serve as a credible placebo intervention as it mimics the web-based patient contact inherent in *d*CBT-I, but is inert with respect to sleep outcomes.⁸⁴ As with the *d*CBT-I group, these topics will be divided equally across 6-8 weekly sessions.

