Those without insomnia remission following *d*CBT-I (ISI > 10)⁶⁸ treatment (typically 40%) will be randomized to standard face-to-face CBT-I treatment or attention control during this second phase of the SMART design. Treatments will be done at sites spread across the Detroit Tri-county area by psychologists certified in behavioral sleep medicine. For all groups, research assessments (sleep and depression) will be obtained at pre-treatment baseline, post-treatment 1 (~8 weeks following initiation of *d*CBT-I), post-treatment 2 (~8 weeks following face-to-face CBT-I initiation), and follow-up. The 1 year follow-up research assessments will include assessment of depression incidence and relapse occurring at any point throughout the previous 12-month period before the respective assessment. Moderation variables (i.e., sleep-reactivity, demographics) will be collected at baseline and mediation variables (i.e., nocturnal rumination) will be measured at each post-treatment and follow-up research assessment for all groups.

We will align with the following recommendations for effectiveness trials with minimal exclusion criteria to ensure a diversity of the sample representative of the population encountered in clinical practice.⁷⁵ We will only exclude those unwilling to participate, under the age of 18, those already on antidepressants, those already known to be harmed or not benefitted by one of the CBT-I interventions, known sleep disorders by EMR (e.g. sleep apnea, narcolepsy) and untreated medical or psychiatric disorders. Additionally, during the initial screening, those with depression (PHQ-9 or QIDS moderate) will be excluded.

Overall, we are assuming an attrition rate of approximately 30%, Although trial participants will be predominantly recruited through our network of primary care sites (31 in 2016), we will mitigate recruitment shortfalls through the HFHS Sleep Center patient registry (>20,000 insomnia patients). Participants will receive a stipend of \$20.00 per assessment and follow up.

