We will also test treatment effects on quantitative sleep parameters including ISI, sleep onset latency (SOL), wake after sleep onset (WASO), and sleep efficiency collected using standardized report-based measures. Sleep diary data will be collected as part of the standard of care during each treatment to analyze trends across time.⁹¹ Depression outcomes will be measured by the 16-item Quick Inventory of Depressive Symptomatology (QIDS),⁷⁷ which is more extensive than the PHQ-9 and will be measured pre- and post-treatment during an online assessment following screening. As sleep is a component of the QIDS assessment, items relating to insomnia will be removed for all analyses (see below). Both study entry and case identification will include QIDS criteria for chronic nonpsychotic, major depressive disorder.⁷⁷ To enter the study participants will need to score less than an 11 on the QIDS. During year 1 follow-up, MDD cases will be identified (new onset, recurrence) for those who meet criteria of greater than or equal to 13 or a lower sub-threshold cut off greater or equal to 11 to increase sensitivity.^{77,82}

TARGETS

Rumination (mediator): refers to the perseveration of negatively-valenced thoughts, which critically increases risk for depression.⁹³ To test the possibility that insomnia-induced rumination serves as a risk factor for depression, we will include a state rumination measure at the post-treatment assessment to be used in a separate mediation model to test for the possibility that rumination is a primary component in the development of depression in individuals with insomnia. The target (mediator) in the proposed studies is state-rumination, specifically, nocturnal rumination which will be assessed using the Thought Control Questionnaire Insomnia-Revised (TCQI).⁹⁸ Whereas good sleepers get an adaptive reprieve from rumination at bedtime, insomnia extends rumination into the night.¹⁰⁶ Further, the inability to fall asleep at night can itself trigger negative schemas, such as helplessness and lack of control, that provide additional content for rumination.¹⁰⁷ While good sleepers think about '*nothing in particular*', insomniacs engage in nocturnal rumination about daytime stressors or the adverse effects of poor sleep. Insomnia may thus be a key contributor to nocturnal rumination.¹⁰⁸ Yet, no prior study has investigated rumination as a modifiable component of insomnia that when attenuated may lead to reduced MDD risk (Specific Aim 3).

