Sleep reactivity¹²⁰(moderator): may moderate the effects of sleep improvement on depression. **Identifying a significant moderator(s) of treatment impact could lead to the development of cost-effective strategies to triage those at**

Research Strategy

greatest risk for depression into effective preventative programs of treatment. This directly aligns with NIMH's Strategic Objective 3, which is to identify focused and impactful *preventative* interventions. One risk factor linked to both insomnia and depression is the heritable trait of sleep reactivity.^{122,123} Sleep reactivity is a trait predisposition to insomnia that manifests as a *sleep system* that is over-sensitive or “over-reactive” to stress.¹²⁰ The Ford Insomnia Response to Stress Test (FIRST)¹²⁴ is a psychometrically and biologically validated instrument used to measure sleep reactivity. It is expeditious and cost-effective, minimizing burden in both research and clinical settings. Substantial evidence demonstrates reliability, validity, and utility for the FIRST. Longitudinal studies have shown high sleep reactivity (FIRST) increase the risk of new onset insomnia and predict the chronicity of insomnia in good sleepers up to 3 years later.^{24,132-134}

Aim 1: analysis will be on the post-treatment impact on RDoC sleep outcomes (ISI) and QIDS of the internet-based dCBT-I, followed by the more **personalized face-to-face** CBT-I group compared to the attention control group. Quantitative sleep measures, SOL and WASO, will also be assessed. A linear mixed model will examine the post-treatment sleep values using the baseline covariates. **Aim 2:** A comparison of face-to-face versus attention control will use an analogous statistical methodology as described above for Aim 1.

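### After the second randomisation, the unweighted model for Aims 1 and 2 does not in general estimate the stepped-care effect, and no model suited to yes/no 1-year depression is named

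*Combined protocol and SAP*

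**What the plan says.** The Aim 1 analysis paragraph of the Research Strategy states that "analysis will be on the post-treatment impact on RDoC sleep outcomes (ISI) and QIDS of the internet-based dCBT-I, followed by the more" personalised face-to-face CBT-I group will be set against attention control. The model is given in one sentence: "A linear mixed model will examine the post-treatment sleep values using the baseline covariates". The next sentence, labelled Aim 2, reads: "A comparison of face-to-face versus attention control will use an analogous statistical methodology as described above for Aim 1".

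The second-phase paragraph says that dCBT-I non-remitters (typically 40%) "will be randomized to standard face-to-face CBT-I treatment or attention control during this second phase of the SMART design". Remitters are not re-randomised.

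The specific aims put a stepped-care question for depression. Aim 2 concerns dCBT-I and "CBT-I using a stepped care model for prevention of" incident depression and relapse, and continues: "These aims will be tested by comparing the 1-year rate of depression outcomes of both" treatments with attention control. The outcome paragraph before the TARGETS heading defines the 1-year outcome by case: "MDD cases will be identified (new onset, recurrence) for those who meet criteria" on the QIDS.

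On missing data the text gives only an expectation: "Overall, we are assuming an attrition rate of approximately 30" per cent. Q-learning appears under the Aim 3 analysis, for choosing the second-phase option among non-remitters.

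**The concern.** In the treated arm, remitters keep a single path while non-remitters are split in two. Those who follow the regimen of dCBT-I, then CBT-I if not remitted, are the remitters plus only a fraction of the non-remitters. A model with baseline covariates and no weights does not restore the missing fraction. The text does not say whether remitters belong to the sequential group, or where non-remitters re-randomised to attention control are counted.

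The analyst would have to choose among groups that answer different questions, possibly after seeing the data. One choice dilutes any CBT-I benefit. Another over-represents people who had already done well on dCBT-I. For depression there is a second gap: a linear model of sleep values is not a model for a yes/no outcome at 1 year.

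**Working it through.** **Inputs from the documents.** 500 enrolled with at least 250 per group (2 × 250 = 500, consistent); 40% non-remission; about 30% attrition. No power calculation, effect size or event rate is given, so there is no further figure to reproduce.

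**Assumptions.** Second-phase probability of CBT-I, p = 1/2, with 2:1 and 1:2 (CBT-I:control) as the range. D is the effect of dCBT-I alone. G is the gain from CBT-I over attention control in non-remitters.

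**Composition at 1:1.** The treated arm of 250 yields 150 remitters, 50 non-remitters on CBT-I and 50 on attention control. Remitters plus CBT-I recipients number 200, so remitters are 150/200 = 75% of that group. Under the regimen they should be 60%. Weighting the 50 by 2 gives 150/(150 + 100) = 60%.

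**Whole arm.** Stepped care is D + 0.4G. The whole arm estimates D + 0.4pG. The shortfall is 0.4(1−p)G, which is zero if G = 0. For an assumed G of 2-4 ISI points it is 0.40-0.80 at 1:1, 0.27-0.53 at 2:1 and 0.53-1.07 at 1:2.

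**Large-sample check.** D = 2, SD 5, equal correlations of 0.3-0.8 between visits, 1:1, no dropout, model adjusted for baseline only:

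| G | True effect | Whole arm | Remitters + CBT-I, unweighted | Same group, weighted |
|---|---|---|---|---|
| 3 | 2 + 0.4 × 3 = 3.2 | 2.6 | 3.0-3.1 | 3.2 |
| 0 | 2.0 | 2.0 | 2.2-2.3 | 2.0 |

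The unweighted group understates the effect when G = 3 and overstates it when G = 0. At G = 2 (true 2.8) it is close to right. Its bias depends on the model as well as on G.

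**Depression, illustration.** Assume 1-year rates of 5% in remitters, 15% in non-remitters on CBT-I and 20% in non-remitters on control.
- Regimen, weighted: 0.6 × 5 + 0.4 × 15 = 9.0%.
- Remitters plus CBT-I, unweighted: (0.6 × 5 + 0.2 × 15)/0.8 = 7.5%.
- Whole arm: 0.6 × 5 + 0.2 × 15 + 0.2 × 20 = 10.0%.
- CBT-I recipients only: 15.0%.

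If all three rates are equal, the four answers coincide.

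**Dropout.** In a simulation with G = 3 (true 3.2) and 31-33% dropout that rises with post-treatment 1 ISI (assumed), the whole arm gave 2.4-2.5 and the weighted analysis of observed cases 2.9-3.1. The weighted analysis with dropout weights or multiple imputation gave 3.2.

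**Price of weighting.** Effective n is 250/(0.6 + 0.4/p): 179 at 1:1, 208 at 2:1 and 139 at 1:2. The standard error of the difference from control, relative to the whole arm, is √((1.6 + 0.4/p)/2): 1.10, 1.05 and 1.18. At 1:1 the weighted test gains power only if (D + 0.4G)/(D + 0.2G) exceeds 1.095, that is, if G is above about 0.53D.

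**The case against.** The strongest reply is that the plan never commits to the harmful reading. A reader might infer that the whole-arm result will be reported as the stepped-care effect, so that benefit will be understated. No section says so; the text names a sequential group instead, and the whole-arm contrast is valid for first-stage assignment. The whole-arm shortfall is therefore the size of one possible error, and the unweighted alternative can err in either direction by a smaller amount.

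A second reply is that the aims are ambiguous. Aim 1a opens as a question about dCBT-I, and Aim 2 can be read as two component comparisons. That stands for Aim 1a, where stepped care is one reading. Aim 2 names a stepped-care model outright.

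Third, a reader might infer that depression has no analysis at all. That goes too far: the aims name the 1-year rate and the comparator, and a sentence labelled Aim 2 points to an analogous method. That sentence is most naturally face-to-face versus control among re-randomised non-remitters, and the method it borrows is a linear model for sleep values. What is missing is a model that suits the outcome and a defined group.

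Fourth, Figure 1 is not shown and may give the second-phase ratio, so the ratio is treated here as an assumption and not as an omission. A flow diagram is unlikely to supply weights or a binary model. Q-learning does not fill the gap, because it addresses a different, exploratory question.

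**Conclusion.** The point holds for outcomes after the second randomisation. Analysed without weights, the sequential group does not in general give the effect of stepped care versus control. At an assumed 1:1 and D = 2, the error is about −0.6 ISI points for the whole arm at G = 3 and zero at G = 0. For unweighted remitters plus CBT-I recipients it runs from about +0.3 at G = 0 to −0.2 at G = 3. Only the 40%, the 250 per group and the 30% come from the documents; effects, SD, correlations, allocation, depression rates and dropout pattern are assumed. That group membership is left open, and that a linear model for sleep values does not fit yes/no cases, needs no assumption.

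The documents do not support the wider inference that the trial's comparisons are all compromised. dCBT-I versus control at post-treatment 1 is sound, and so is face-to-face CBT-I versus attention control among re-randomised non-remitters. This is a cheap improvement.

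**What to change.** In the Aim 1 and Aim 2 analysis text, and for the Aim 2 comparison in the specific aims, add for post-treatment 2 and 1-year outcomes:

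1. Define the regimen of dCBT-I, then CBT-I if not remitted, as remitters plus non-remitters assigned to CBT-I.
2. Compare it with first-stage control by baseline-adjusted regression with robust standard errors. Use weight 1 for remitters and first-stage controls, and 1/(second-phase allocation probability) for the non-remitters. Standardising to the true remitter share is an acceptable alternative.
3. Use a binary-outcome model for 1-year depression.
4. Keep the whole-arm contrast, labelled as the effect of first-stage assignment.
5. Participants who miss post-treatment 1 have no remission status and so no weight. Use multiple imputation or dropout weights for the expected attrition.

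The non-remission definitions must also be reconciled. Aim 1a gives ISI above 10 or a reduction of less than 8 points; the second-phase paragraph gives ISI above 10 alone. They decide who is re-randomised and weighted.

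The cost is wording and modest programming, with no extra data. The price is precision: at 1:1 the standard error is about 10% larger than for the whole arm, and power is lower when the CBT-I gain is below about half of the dCBT-I effect. In the dropout simulation, dropout weights or imputation added a further 2-10% when dropout depended on ISI.

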We propose a large-scale clinical trial in primary care utilizing a stepped-care model to determine the *effectiveness* of *d*CBT-I alone or in combination with traditional face-to-face cognitive behavioral therapy for insomnia (CBT-I), and the effects of these established sleep interventions on the prevention of depression. This stepped care trial utilizes a “SMART” design by randomizing to internet-based *d*CBT-I or an attention-control group. Following this phase, a second randomization to face-to-face *clinician-based* CBT-I or attention control will be provided to patients who do not respond to *d*CBT-I. The present trial represents an innovative combination of these insomnia therapies with potential for real-world implementation and scalability. Another important and unique component of the trial is the 1-year follow-up assessment of participants to determine the durability of digitally- and traditionally-delivered behavioral insomnia treatments over time, and to fully assess the impact on prevention of incident depression and relapse.

The goals of this trial will be to 1) determine the relative *effectiveness* of *d*CBT-I alone or in combination with clinician-based CBT-I in non-depressed insomniacs and 2) to test the effects of these sleep interventions for preventing depression incidence and relapse. Moderators of the effects including sleep reactivity, rumination, race, and SES will be assessed.

We will deliver *d*CBT-I to individuals with insomnia disorder, and add face-to-face CBT-I for non-remitters. We will compare sleep outcomes and depression rates to a control group at post-treatment, and then at 1 year follow-up.

Aim 1a) Assess the acute and long-term effectiveness of *d*CBT-I on RDoC sleep parameters: Insomnia Severity Index (ISI), sleep onset latency (SOL) and wake after sleep onset (WASO) in an insomnia cohort including those at elevated-risk for depression (high sleep reactivity, low SES, minority). This aim will be tested by administering internet-based *d*CBT-I to people with insomnia and adding CBT-I in non-remitters (ISI > 10 or < 8 point ISI reduction), as well as comparing the RDoC sleep outcomes to an attention control group post-treatment and at 1 year follow-up.

Aim 1b) Determine the acute and long-term effectiveness of using face-to-face CBT-I to treat insomnia in non-responders on RDoC sleep outcomes (ISI, SOL, WASO) relative to a comparison group post-treatment and at 1-year follow-up.

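### The only analysis entry labelled Aim 2 does not match the Aim 2 objective: it describes a second-stage contrast in about 100 of 500 participants, with a model written for sleep values rather than a 1-year depression rate.

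*Combined protocol and SAP*

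**What the plan says.** All references are to the combined protocol and SAP.

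- **Specific aims, Aim 2.** The aim concerns stepped care and has two parts, incident depression (2a) and relapse (2b). On testing it says: "These aims will be tested by comparing the 1-year rate of depression outcomes of both" dCBT-I and CBT-I, with an attention control group as comparator. The text after the trial goals agrees: "We will compare sleep outcomes and depression rates to a control group at post-treatment, and then at 1 year follow-up".
- **Research Strategy, design.** At least 250 participants per group are first randomised to dCBT-I or attention control. Those not in remission after dCBT-I, typically 40%, "will be randomized to standard face-to-face CBT-I treatment or attention control during this second phase of the SMART design". The allocation ratio of this second step is not given.
- **Research Strategy, assessments.** The 1-year visit includes "assessment of depression incidence and relapse occurring at any point throughout the previous 12-month period" before that visit. Attrition of about 30% is assumed.
- **Research Strategy, depression outcomes.** A case is a QIDS score of at least 13, or of at least 11 as a lower, sub-threshold cut-off meant to raise sensitivity. The same paragraph says that QIDS "items relating to insomnia will be removed for all analyses".
- **Analysis paragraph, Aim 1.** It names ISI and QIDS after treatment, for dCBT-I followed by face-to-face CBT-I against attention control. The one model named is a linear mixed model of post-treatment sleep values with baseline covariates.
- **Analysis paragraph, Aim 2.** One sentence: "A comparison of face-to-face versus attention control will use an analogous statistical methodology as described above for Aim 1".

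**The concern.** Depression prevention is the question in the trial's title. The aims promise a comparison of 1-year depression rates for a stepped-care programme. The analysis entry carrying that label compares something else, in a subgroup defined after first-stage treatment, with a method written for a continuous sleep outcome. Followed literally, the plan would estimate what face-to-face CBT-I adds among people in whom dCBT-I did not bring remission. It would not estimate what the programme does for depression over a year.

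Several analyses could fill the gap: as first randomised, by treatment strategy, or second stage only, each with either QIDS cut-off. They answer different questions. If the choice is left open, the headline depression result can be chosen after the data are seen.

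**Working it through.** **Plan's own figure.** Enrolment is 500 = 250 + 250. No significance level, power, effect size or depression rate accompanies it, so it cannot be reproduced. The counts below take 250 per arm, 40% non-remission and 30% attrition from the documents. A 1:1 second stage is assumed.

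**1. Who enters the contrast labelled Aim 2.**
- Re-randomised: 250 × 0.40 = 100, or 50 per arm. If non-remission were 30% to 50% (assumed range): 75 to 125.
- Left out: 250 × 0.60 = 150 remitters plus 250 first-stage controls = 400 of 500.
- After 30% attrition: 100 × 0.70 = 70, or 35 per arm.

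**2. Does the sentence match the objective?**
- Outcome: the aim is a case rate over 12 months; the borrowed model is for post-treatment sleep values.
- Comparison: the aim covers dCBT-I and CBT-I against control; the sentence covers face-to-face CBT-I only.
- Population: the aim concerns the stepped-care programme; the sentence, on its natural reading, concerns non-remitters only. It fits Aim 1b, which concerns face-to-face CBT-I in non-responders, better than Aim 2.

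**3. How the candidate analyses differ.** Let r_R be the 1-year risk in remitters, r_F in non-remitters allocated to face-to-face CBT-I, r_A in non-remitters allocated to attention control, and q the probability of allocation to CBT-I.
- Strategy 1 (dCBT-I, then CBT-I if no remission): 0.6 r_R + 0.4 r_F.
- Strategy 2 (dCBT-I without added CBT-I): 0.6 r_R + 0.4 r_A.
- dCBT-I arm as first randomised: 0.6 r_R + 0.4[q r_F + (1 − q) r_A].
- Arm minus strategy 1 = 0.4(1 − q)(r_A − r_F). With q = 1/2 the factor is 0.20; with q = 1/3 or 2/3 it is 0.27 or 0.13.

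So if CBT-I helps, the as-randomised comparison understates strategy 1 by 0.20 times the second-stage effect at 1:1. It overstates strategy 2 by 0.4 × 0.5 = 0.20 times that effect.

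**4. Precision of a weighted strategy comparison.** Each strategy against control uses 250 + 150 + 50 = 450 of 500. With even 30% attrition there are 175 per arm: 105 remitters and 35 + 35 non-remitters. Weights are 1 for remitters and 2 for the 35 non-remitters consistent with the strategy.
- Equal risk in remitters and non-remitters: effective size = (105 + 2 × 35)² / (105 + 35 × 4) = 30,625/245 = 125. Ratio of standard errors to the as-randomised comparison = √[(1/125 + 1/175)/(2/175)] = √1.2 = 1.095.
- Overall risk 10%, non-remitters at twice the remitters' risk: r_R = 0.10/1.4 = 0.0714, r_N = 0.1429. Variance of the strategy arm = [105 × 0.0671 + 140 × 0.1243]/30,625 = 0.000798, against 0.09/175 = 0.000514. Ratio = √[(0.000798 + 0.000514)/(2 × 0.000514)] = 1.130.
- Over risks of 10–20% and risk ratios of 1 to 2, with no second-stage effect, the range is 1.095 to 1.130.

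**5. Illustration of information lost.** Power to detect a halving of an assumed control rate, two-sided 5%: Φ{[Δ√n − 1.96√(2p̄(1 − p̄))]/√(p₁(1 − p₁) + p₂(1 − p₂))}. For 20% versus 10%:
- n = 35 per arm: (0.592 − 0.990)/0.5 = −0.80, power 21%.
- n = 175 per arm: (1.323 − 0.990)/0.5 = 0.67, power 75%.

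For control rates of 10% and 30%, the pairs are 12% against 43% and 32% against 92%. The two contrasts estimate different effects, so this shows only how much information each carries.

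**The case against.** **Much of the estimand is already there.** A reader might infer that Aim 2 has no stated model or estimand. The documents do not support that. Outcome, 12-month window, comparator and case thresholds are given, and a model is stated by reference. What remains is narrower: the referenced model does not suit a case rate, and there is no effect measure, no statement of which strategies are compared, and no rule for combining remitters with re-randomised non-remitters.

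**Attention control could mean the first-stage group.** The term is used for both comparators, and the Aim 2 sentence does not say which. The second-stage reading is the more natural one but not certain. The other reading does not rescue the sentence, because selected non-remitters against all first-stage controls is not a randomised comparison.

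**It may be a labelling slip.** If the sentence was meant for Aim 1b, then 100 of 500 does not size any planned depression analysis. That is fair, but the Aim 2 analysis is then unwritten and the same repair is needed.

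**A weighted strategy analysis need not be the main one.** This stands. The aims speak of both interventions, the goals speak of dCBT-I alone or in combination, and nothing ranks one strategy above the other or above the comparison as first randomised.

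**The case definition is partly settled.** Calling 11 sub-threshold suggests that 13 is the main cut-off. Whether the cut-offs apply with the insomnia items removed is still not stated.

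**Conclusion.** The concern holds in this form: the Aim 2 objective is stated, but the analysis entry bearing its label does not address it. On the natural reading it uses about 100 of 500 participants (about 70 after attrition) and a model unsuited to a 1-year case rate. As Aim 2 is the title question, this should be corrected before analysis.

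Two inferences go too far. The second-stage contrast is not invalid: it is randomised and can serve as the CBT-I component of Aim 2. Nor is the as-randomised comparison wrong: it answers a different question, differing from the full stepped-care strategy by about 0.20 times the second-stage effect.

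The mismatch rests on the text alone. The counts rest on the plan's 40% and 30%. The 0.20 and the weight of 2 rest on an assumed 1:1 second stage, and the precision cost on the risks assumed above.

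**What to change.** In the analysis paragraph:

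1. Label the existing sentence as the second-stage comparison among re-randomised non-remitters: Aim 1b for sleep, and the CBT-I component for depression.
2. Add the Aim 2 analysis: depression case at 1 year as a binary outcome, with a binary-outcome model giving risk difference and risk ratio with 95% confidence intervals.
   - (a) All participants as first randomised, dCBT-I arm against control.
   - (b) Each embedded strategy (dCBT-I then CBT-I if no remission; dCBT-I without added CBT-I) against the first-stage control arm. Weight 1 for controls and for dCBT-I participants never re-randomised, including early leavers. For re-randomised participants consistent with the strategy, use the inverse of their allocation probability (2 if 1:1); for the others, 0. Use robust standard errors.
   - State in advance which of (a) and (b) is the main analysis, and state the second-stage allocation ratio.
3. Report 2a and 2b separately if depression history is recorded at baseline.
4. Name the primary QIDS cut-off and say whether it applies with or without the insomnia items.
5. Reconcile the two definitions of non-remission, since they decide who is re-randomised and hence the weights: Aim 1a uses ISI above 10 or a reduction of less than 8 points; the Research Strategy uses ISI above 10 alone.

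**Cost.** Wording and programming; no added patients or visits. Splitting 2a from 2b may need one baseline item, feasible only for participants not yet enrolled, and leaves fewer events in each part. Intervals for (b) are roughly 10–13% wider than for (a) under the assumptions above. The weights for early leavers do not deal with missing 1-year outcomes, which need their own rule.
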